2.7 Patient Information and Informed Consent

Co-investigators will explain to each participant the nature of the study, its purpose, the procedures involved, the expected duration, the potential risks and benefits and any discomfort it may cause. Participants will be informed that the participation in the study is voluntary and that they may withdraw from the study at any time without affecting their care. They will also be informed that their participation in the study will not be remunerated.

Participants will be informed that their medical files may be examined by authorised individuals other than their treating physician.

Participants will be briefly informed by the co-investigators at the beginning of the study. Indeed, mentioning that the study aims to investigate the effects of communication on pain and anxiety and

that two messages with different content will be tested could create expectations and skew the results of the study. Thus, the co-investigators will only collect their verbal consent at this stage. The content of this partial verbal information will be based on the partial information template (Appendix 1).

A complete information sheet describing the study and the information needed for participants to make an informed decision about their participation will be provided once the data have been collected, along with a consent form (Appendices 2 and 3). Participants will have at least 15 minutes to make a final decision on whether or not to participate in the study and, if so, sign the consent form. In the event that participants refuse to sign it, their data will be physically destroyed using a shredder, except for data relating to their sex and age. These data will be kept for statistical purposes in a separate document (Appendix 7). The consent form will also be signed and dated by one of the co-investigators and will be an integral part of the study documents. Participants will be provided with a copy of the signed consent form.

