6. STUDY DESIGN

6.1 General study design and justification of design

It is an interventional, prospective, randomized, active-controlled, monocentric intervention study. It will take place in the LUH ED between October 2017 and October 2019. All patients admitted to this service will be eligible for inclusion. Data collection will be possible every day of the week between 7am and 10 pm in order to obtain a sample that is as representative as possible of an ED's population. In order to be able to cover as many hours as possible, the co-investigators will divide them among themselves and, at each intervention, only one of them will be present. Dr [name] and Dre [name] will not participate in data collection.

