After consulting the patient's medical records in the ED and checking with the patient's caregivers that there are no exclusion criteria, the co-investigators will introduce themselves to the patients and invite them to participate in the study. The co-investigators will explain to the patients that, given the fact that their medical care involves the insertion of a PIC, they are eligible for this study aimed at improving the care of patients visiting the LUH ED during such an act. Should patients require additional information, the co-investigators will simply state that the study's primary objective is to assess the technical characteristics of the PIC insertion. At this stage, only a verbal agreement will be required. After verifying that all inclusion criteria have been met, that none of the exclusion criteria are applicable and obtaining a verbal consent, patients will be randomized in a 1:1 ratio between the two arms of the study, in a double-blind design (patient, caregiver, co-investigator) in the first phase and in a single-blind design (patient) in the second phase. The co-investigators will collect some additional data in a standardized manner by following the CRF and then report to the caregivers that they can prepare the patients for PIC insertion (installation of the tourniquet, vein tracking and site disinfection). In the first phase, a test audio clip and a recorded introductory audio clip will be played to the patients before the caregivers prepare them for the procedure. Once these preparations are completed, the co-investigators will play the recorded audio intervention or control message to the patients in the first phase or the caregivers will deliver one of the two alternative messages directly before puncturing the patients' vein in the second phase. In both cases, the co-investigators will complete the collection of data according to the CRF, first from patients and then from caregivers. Once all the data has been collected, a complete information sheet and consent form will be provided to the patients, along with additional explanations when requested. Patients will have a minimum of 15 minutes to sign the consent form. Excluding this 15 minutes reflection period, participation in the study should not exceed 20 minutes and will be unique.

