6.2 Methods of minimising bias

6.2.1 Randomisation

In the first phase of the double-blind study, a randomization method by permutation of blocks of 4 and 6 patients will be used. The principal investigator, who will not collect data, will create the randomization list and hold the randomization seed.

In the second phase, only patients will be blind, but the assignment of one of the two messages will also be done by block permutation of 4 and 6.

In both phases of the study, randomization will occur immediately after verbal consent, before the intervention or control message is delivered.

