6.2.2 Blinding procedures

During the first phase, the allocation of the arm « control message » or of the arm « intervention message » will be determined by a code written on a card inside a sealed and opaque envelope, prepared by the principal investigator. This code will indicate the number, between 1 and 130, of the audio track to be played to the patient and will be recorded in the CRF. In the second phase, the note « control message » or « intervention message » written on the card will indicate to the caregivers the message to be delivered and will be reported in the CRF. Envelopes will be numbered consecutively, and the co-investigators will open them consecutively, noting each time the opening date. The principal investigator will regularly verify that the order of opening is respected by checking the number of envelopes opened and the opening dates against the number of patients included in the study.

The first phase of the study will be carried out in double blind (patient, caregiver, co-investigator) thanks to the coding of audio recordings. In the second phase, only patients will be blinded to the tested component.

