11.4.2 Primary Analysis

The primary analysis will compare the pain intensity and unpleasantness after the PIC insertion as measured by VAS. The VAS will be compared by Student t-test if the distribution is Gaussian or by Wilcoxon rank sum test if not. The analysis will be conducted according to the « intention to treat » principle, which will include all randomized patients.

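### The primary analysis is described as intention to treat on all randomised patients, but post-randomisation refusers' outcomes are destroyed and no rule covers a missing primary outcome

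*Combined protocol and SAP*

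**What the plan says.** Section 11.4.2 commits the primary comparison of pain intensity and unpleasantness to the intention-to-treat "principle, which will include all randomized patients".

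The order of events is set out in Sections 6.1 and 6.2.1. In both phases, "randomization will occur immediately after verbal consent, before the intervention or control message is delivered". Then, from Section 6.1, "Once all the data has been collected, a complete information sheet and consent form will be provided to the patients". Section 2.7 explains why: telling patients the aim beforehand could skew their ratings.

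Section 2.7 continues: "In the event that participants refuse to sign it, their data will be physically destroyed using a shredder". Sex and age are kept. Sections 7.4, 8.5 and 9.2.3 apply the same rule to patients who revoke or are excluded, and Section 7.4 allows exclusion up to signature of the form.

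Section 11.2 allows 10% for missing values or refusal after randomisation and so randomises 60 per arm. Sections 7.4 and 11.5 count lost patients towards the recruitment target. Section 11.5 rules out imputation for data other than the primary endpoint and is silent on the primary endpoint. Section 6.2.3 keeps sex and age to compare lost with included patients. Section 11.4.6 promises that deviations from the statistical plan will be reported.

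**The concern.** The analysis set named in Section 11.4.2 is one the design cannot deliver. A randomised patient who declines to sign has no outcome left to analyse, so the primary analysis covers only patients who consented in writing and have an outcome.

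This matters because the loss may not be random. Refusal or late revocation is decided after the patient has heard the message, had the puncture and been told the purpose, so it could depend on both the arm and the pain felt. Blinding in phase 1 limits any staff influence on that decision. Phase 2 has less protection: "In the second phase, only patients will be blinded to the tested component". Of the co-investigators, "at each intervention, only one of them will be present", and that person handles consent knowing the allocation.

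Destroyed outcomes cannot be recovered. If losses are not shown by arm and no sensitivity analysis is planned, a reader cannot judge how far the result extends to everyone randomised. The 10% mark-up protects power; it does not protect the comparison.

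**Working it through.** **Inputs.** From Section 11.2: SD 24 mm (given for intensity only), target difference 13 mm, alpha 5%, power 80%, 10% loss, 60 randomised per arm. Assumed here: a two-sided t-test, and a 12 to 24 mm excess in lost patients (half to one SD). The documents give no figure for that excess.

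**The plan's own figure.** n per arm = 2 × (1.960 + 0.842)² × 24² / 13² = 53.5, so 54 by the normal approximation. The t-test gives power 79.6% at 54 and 80.4% at 55, so the stated 55 reproduces. With 10% lost, 60 × 0.9 = 54 per arm are analysed. The sample size is not in dispute.

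**Shift from selective loss.** If a fraction f of an arm is lost and those patients average δ above that arm's full mean, the retained mean lies f × δ / (1 − f) below the full mean.

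- f = 0.10, δ = 12: 1.2 / 0.9 = 1.33 mm
- f = 0.10, δ = 24: 2.4 / 0.9 = 2.67 mm
- f = 0.05, δ = 12 or 24: 0.6 / 0.95 = 0.63 mm or 1.2 / 0.95 = 1.26 mm
- the same shift in both arms: the shifts cancel and there is no bias

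**Effect on the test.** Take 10% lost in both arms, selectively in one only, with 54 analysed per arm. The standard error is 24 × √(2/54) = 4.62 mm, with 106 degrees of freedom.

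| Shift (mm) | Against the intervention: power at a true 13 mm | In its favour: chance of a significant benefit with no true effect |
|---|---|---|
| 0 | 79.6% | 2.5% |
| 1.33 | 70.6% (expected difference 11.67 mm) | 4.7% |
| 2.67 | 60.1% (expected difference 10.33 mm) | 8.3% |

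**Tipping point.** Suppose 6 of 60 intervention patients are lost and average x mm above those retained, while lost controls match retained controls. The difference among all randomised is D − 0.1x. The pooled variance is about 576 + 0.1 × 0.9 × x² / 2 = 576 + 0.045x². The smallest significant difference is 1.980 × √(2/60) × √(576 + 0.045x²).

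- D = 13: at x = 38.4, 13 − 3.84 = 9.16, and the threshold is 1.980 × 0.1826 × 25.35 = 9.16. Slightly different variance conventions give 38 to 39 mm.
- D = 10 (t = 10/4.62 = 2.165, p = 0.033): at x = 12.7, 10 − 1.27 = 8.73, and the threshold is 1.980 × 0.1826 × 24.15 = 8.73. The answer is about 13 mm.

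**The case against.** The strongest reply is that the plan hides nothing. It discloses the loss and enlarges the sample for it, calls these patients missing data, keeps sex and age for comparison, and promises to report deviations. Destroying refusers' data follows from seeking full consent after the event and is not an error in itself. Someone reading Sections 11.2, 11.4.2 and 11.5 together would expect an analysis of consenting patients. Much of this stands. It does not make the wording of Section 11.4.2 true, and it does not supply a rule for the primary outcome. Reporting a deviation afterwards is also not prespecification.

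Some stronger readings are tempting but not supported:

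- *Losses by arm cannot be recovered because Section 11.4 deletes the patient number before analysis.* Any comparison of arms needs an arm label in the analysis file. The principal investigator holds the list, and "Envelopes will be numbered consecutively, and the co-investigators will open them consecutively, noting each time the opening date". Losses by arm follow by subtraction.
- *The sex and age check ignores the arm.* Section 6.2.3 does not say either way, and Appendices 7 and 8 appear only as titles.
- *Every excluded patient had an outcome that was destroyed.* Several exclusions in Section 7.4 concern knowledge gained before the intervention. If applied then, no post-insertion score exists. The selection concern applies mainly to refusals and late revocations, whose share of the 10% is not given.
- *The power figures describe loss in one arm only.* They do not. With 54 and 60 analysed, power would be 81.7%, falling to 72.9% or 62.4%.

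It is also fair that the 12 to 24 mm excess has no source in the documents, and that the figures assume a t-test although Section 11.4.2 allows the Wilcoxon test.

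**Conclusion.** The point holds, and it should be fixed. Section 11.4.2 names a set that cannot be analysed once any randomised patient's data are destroyed, and the plan expects losses of this kind. Section 11.5 leaves the primary outcome without a missing-data rule. Both conclusions rest on the text alone.

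The size depends on assumptions: a t-test, SD 24 mm for intensity, losses that are selective in one arm, and an assumed excess in the lost patients. The 10% is an upper case for destroyed data, because it also covers ordinary missing values. For a result at the design difference the risk is small, since six lost patients would have to score nearly 40 mm above those retained. For a result near the threshold, such as 10 mm, about 13 mm is enough. A reader might infer that the trial's result will be biased or that the consent procedure is wrong; the documents support neither.

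**What to change.** 1. **Section 11.4.2.** Replace the reference to all randomised patients with: *all randomised patients with written consent and a retained outcome, analysed in their allocated arm*. Do not describe this as full intention to treat.
2. **Loss report.** After unblinding, report losses by arm and phase as the number allocated among opened envelopes minus the number analysed. This needs no patient-level linkage and no new data on refusers. Give the split into revoked and excluded by arm only if the existing forms allow it; otherwise give totals.
3. **Section 11.5.** State that the primary analysis uses available cases. Prespecify one tipping-point analysis on the mean difference: shift the mean of lost patients in each arm over a stated range, for example 0 to 40 mm in either direction and kept within the 0 to 100 mm scale, and report where the conclusion changes. If the Wilcoxon test is used, present this as a supplementary analysis of means. Worst-case bounds would say little: at 10% loss per arm and an observed 13 mm they run from 0.9 × 13 − 10 = 1.7 to 0.9 × 13 + 10 = 21.7 mm.

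The cost is wording in two sections, one table from records already held, and one extra analysis. No additional patients are needed. The downsides are that the full intention-to-treat label is given up and that the sensitivity range is itself an assumption.

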11.4.3 Secondary Analyses

The secondary analysis will compare the pain intensity and unpleasantness after the PIC insertion measured by VAS. The VAS will be compared by Student t-test if the distribution is Gaussian or by Wilcoxon rank sum test if not. The analysis will include only those patients for whom the message has been fully delivered.

The analysis of the secondary objectives, i.e. the intensity of anxiety, also measured by VAS, will focus on the comparison of VAS per Student t-test if the distribution is Gaussian or Wilcoxon rank sum

test if not. The same will be true for the caregivers' assessment by VAS of the patients' pain intensity and unpleasantness and anxiety level at PIC insertion.

11.4.4 Interim analyses

Non-applicable.

11.4.5 Safety analysis

Non-applicable.

11.4.6 Deviation(s) from the original statistical plan

Deviations from the original statistical analysis will be mentioned in the presentation of the results of the study, whether in the form of a Master's thesis or of a scientific paper.

11.5 Handling of missing data and drop-outs

Excluded patients or patients who have revoked their consent will be included in the calculation of the number of participants required to complete the collection of study data, but a 10% mark-up of this number is expected to compensate for these missing data.

For missing data other than the primary endpoint of judgment (pain intensity and unpleasantness after the PIC insertion), no imputation will be performed.

12. QUALITY ASSURANCE AND CONTROL

12.1 Data handling and record keeping / archiving

All data will be collected in paper format.

12.1.1 Case Report Forms

The patient's personal data will be treated by the co-investigators in a confidential and encrypted manner. A CRF (Appendices 4 and 5) and a document containing the patient's personal data (Appendix 6) will be established for each participant, who will be assigned an identification number in order to link these two documents. Only co-investigators will be authorised to complete the CRF and will certify it by signing at the end of each CRF. Any erasure/correction will be marked with the initials of the person making it. The two co-investigators, [name] and [name], will make a double input of the CRF's data into the Excel database to ensure accurate input.

12.1.2 Specification of source documents

The source documents are the complete Patient Information Sheet and Consent Form (Appendices 2 and 3), the CRF (Appendices 4 and 5), the document containing the patient's personal data (Appendix 6), the documents prepared for patients who revoked their consent or were excluded from the study (Appendices 7 and 8), and the document containing the VAS reported by caregivers (Appendix 9).

All source documents will be stored in a secure room at the LUH and then in the principal investigator's office.

12.1.3 Record keeping / archiving

All collected data will be stored in the principal investigator's office for a period of 10 years after the planned or premature completion of the study.

12.2 Data management

The collected data will be entered anonymously into an Excel database. This computerized database will not contain any information identifying the source person. Only the two co-investigators, [name] and [name], will be allowed to enter data into this Excel database. Double data entry will be made to ensure the accuracy of the data. If inconsistencies should arise as a result of this double entry, a follow-up of the changes will be set up for corrections. Data entry can only be made on the computer located in a LUH secure room and the Excel database will be protected by a password known only to the investigators. The database will be saved on an external hard drive that will remain in this LUH secure room until the data collection and entry is completed.

Once the data collection and entry is completed, the database will be deemed complete and cannot be modified. It can then be taken out of the LUH's secure room in order to be statistically analyzed by the principal investigator.

12.3 Monitoring

A research nurse in the LUH ED, will monitor this low-risk clinical trial. It is indeed classified in risk category A and there are no known risks associated with the intervention. Therefore, there will be a monitoring visit prior to the recruitment of the first participant, within one year of the start of the data collection and a closing visit after the end of the data collection.

The purpose of these visits will be to review the various documents and validate compliance with the protocol. The Monitor will verify the following variables for each patient included at the time of the visit: name, surname, first name, date of birth, sex, signed consent form, date of the intervention, message received, possible adverse reactions, main parameters collected (VAS). She will also verify that these variables have been correctly inserted in the database.

Visits will be scheduled according to the availability of each person and the date will be communicated to the co-investigators at least one week in advance. The co-investigators will be available to meet the Monitor and answer her questions. The monitor reserves the right to examine further documents and aspects of the study or to reschedule a visit if she deems it necessary.

If a problem is identified during these visits (e.g. poor coordination between co-investigators, missing documents), the Monitor will share it with the investigators and assist them in solving the problem.

12.4 Audits and Inspections

Study documents, including source documents, will be made available to the CEC or the competent authorities in the event of an audit. Investigators will respond to questions asked during the inspection.

12.5 Confidentiality, Data Protection

The CEC and the competent authorities will have direct access to source documents for monitoring, auditing or inspection. Investigators will have access to all study data except for the coding key for the caregiver study number in the second phase, which will only be known to co-investigators collecting the data and the Monitor. Only anonymised coded data, i.e. all data with the exception of documents containing patients' personal data and those containing the study number of the caregivers, may be made public.

12.6 Storage of biological material and related health data

Non-applicable.

13. PUBLICATION AND DISSEMINATION POLICY

The results of the study will be published in the form of a Master's thesis submitted to the School of Medicine, or in the form of a scientific article submitted for publication to peer-review journals.

14. FUNDING AND SUPPORT

The costs generated by this study will be covered by the Faculty of Biology and Medicine according to the expenses allocated for Master's thesis.

15. INSURANCE

In the event of any damage caused to the participants during this study, the LUH will be liable in its capacity as Sponsor in accordance with the applicable legal provisions.

17. APPENDICES

1. Template for Patient Partial Verbal Information
2. Complete Patient Information Sheet and Consent Form (1st phase)
3. Complete Patient Information Sheet and Consent Form (2nd phase)
4. CRF (1st phase)
5. CRF (2nd phase)
6. Patients' personal data
7. Data (sex and age) of patients who revoked their consent
8. Data (sex and age) of patients excluded from the study
9. Caregivers' VAS
